7 TREATMENTS

Study drug (Racecadotril) will only be shipped to Investigators who have provided the Sponsor (or an authorized representative) with all required study documents, including IEC/IRB approval, and have signed a final study agreement.

7.1 Treatments to Be Administered

Racecadotril Infants Granules for Oral Suspension 10 mg
Racecadotril Children Granules for Oral Suspension 30 mg

1.5 mg/kg of Racecadotril will be administered, 3 times daily (morning, noon, evening), via the oral route.

In infants less than 9 kg: one 10 mg sachet 3 times daily.
In infants from 9 kg to <13 kg: two 10 mg sachets 3 times daily.
In children from 13 kg to 27 kg: one 30 mg sachet 3 times daily.
In children of more than 27 kg: two 30 mg sachets 3 times daily.

Standard treatment for pediatric subjects with diarrhea is oral rehydration solution (ORS). ORS will be given according to the registered local label of the brand and the instruction of the investigator. At the start of the trial, alignment will be reached on the understanding of treatment of standard ORS with the principal investigator with the aim to use the same brand of ORS and the same age-appropriate standardized treatment pattern for the subjects throughout the trial. ORS treatment will be documented in the CRF. Reporting obligations for ORS by the investigator will follow local regulations for marketed products. Racecadotril will be given in addition to ORS.

7.2 Packaging and Labeling

[REDACTED]

[REDACTED]

[REDACTED]

[REDACTED]

[REDACTED]

[REDACTED]

[REDACTED]

[REDACTED]

[REDACTED]

7.3 Storage and Dispensing of Study Drug

All clinical drug supplies are to be stored in a secure, monitored, limited-access area in accordance with labeled storage conditions. The Investigator will maintain accurate records of the disposition of all clinical drug supplies received during the study. These records shall include the amounts of drug supplies and the dates on which drug supplies were received from the Sponsor (or an authorized representative), dispensed to the subject, returned by the subject and returned to the Sponsor (or an authorized representative). If errors or damages in the clinical drug supply shipments occur, the Investigator must contact the Sponsor (or an authorized representative) immediately.

7.4 Method of Assigning Subjects to Treatment Groups

Subjects will be assigned a 5-digit enrollment number . The medication will be identified using 6-digit kit numbers.

The subject numbers will be provided by Clinical Supply Management (Product Development) of Abbott Healthcare Products BV.

7.5 Selection of Doses and Timing in the Study

1.5 mg/kg of Racecadotril will be administered, 3 times daily (morning, noon and evening), via the oral route.

In infants less than 9 kg: one 10 mg sachet 3 times daily.

In infants from 9 kg to <13 kg: two 10 mg sachets 3 times daily.

In children from 13 kg to 27 kg: one 30 mg sachet 3 times daily.

In children of more than 27 kg: two 30 mg sachets 3 times daily.

This dosing regimen is registered by TFDA and described in the SmPC.

Standard treatment for pediatric patients with diarrhea is oral rehydration solution (ORS). ORS will be given according to the registered local label of the brand and the instruction of the investigator. It is recommended that all subjects will be prescribed the same brand of ORS. Racecadotril will be given in addition to ORS.

7.6 Blinding and Treatment Code Information

This is an open-label study; blinding will not be applied.

7.7 Prior and Concomitant Therapy

During the study, subjects are not allowed to be treated with the following treatments:

- Anti-peristaltic drugs, e.g. loperamide
- Antibiotics
- Antipyretics (suppositories)
Oral antipyretics (acetaminophen or ibuprofen) are allowed to be used concomitantly as needed when ear temperature is above 38.3 degrees Celsius, but not longer than two consecutive days during the study. If the fever increases above 39 degrees Celsius with two repeated measurements within one hours, the subject will be withdrawn.
- Intestinal antiseptics, e.g. 8-hydroxyquinoline
- Respiratory decongestants, e.g. phenylephrine
- Antitussive medication, e.g. noscapine
Any antitussive drugs, if indicated for pediatric patients, may be given for temporary relief of symptoms as PRN (administration on as needed basis) except those containing opium alkaloids and derivatives (e.g noscapine).
- Pre- or Probiotics, e.g. fructooligosaccharides, lactobacilli
Subjects on continuous probiotic treatment at study start (e.g. Lactobacillus, Bifidobacterium, yeast) or probiotic-containing supplements/formula of the same product/brand prior to study start can be included. The initiation of pre- or probiotic treatment during the study is forbidden as well as the adaptation of the brand/product or dose.
- Absorbents, e. g. diosmectite, charcoal, pectin, psyllium
- Zinc-containing medication (**other than diaper rash ointments**). **Diaper rash ointments of any kind are allowed.**
- Homemade ORS
ORS will be provided during the study as judged appropriate by the Investigator. Additional intake of self-purchase or self-made ORS is not allowed during the study duration
- ACE Inhibitors
- Antispasmodics
Antispasmodics, indicated for pediatric patients, may be given for temporary relief of symptoms as PRN (administration on an as needed basis) in exceptional cases. If antispasmodics are needed as daily treatment during the study treatment, the subjects should be discontinued.
- Drugs for symptomatic treatment of diarrhea, e.g. pancreatic enzymes, anticholinergic drugs, opiates, diphenoxylate
- Intravenous fluid or electrolyte replacement.

The presence of bloody or purulent stool and fever above 39 degrees Celsius may indicate either the presence of invasive bacteria as a reason for diarrhea or the presence of another severe disease. In addition, Racecadotril has not been investigated in patients with antibiotic-associated diarrhea. Therefore, Racecadotril should not be administered under these conditions.

Subjects who need treatment with the above listed medication should be withdrawn from the study (see section 6).

Dietary modifications for thickening of the stools or yogurt are allowed. If needed, dietary consultation with dietitian or qualified healthcare worker is recommended in order to adapt the diet for thickening of stools or intake of yogurt.

Any intake of other medication is allowed as judged appropriate by the Investigator except those on the list of prohibited medications above.

All medication taken by the subject during the study (from signing the informed consent form through post-study follow-up) is to be recorded on the Concomitant Medication form, except for study drug.

7.8 Treatment Compliance

Drug Accountability

The Investigator is accountable for all clinical drug supplies shipped to his/her study site for the duration of the study. A final accounting of the clinical drug supplies will be required at the completion/termination of the study. The Investigator is required to provide written explanation for any discrepancies.

All used and unused clinical drug supplies will be inventoried and returned to the Sponsor (or an authorized representative) by a designated monitor.

Compliance

Each intake of study drug (Racecadotril) will be recorded in a patient diary and evaluated.

8 STUDY ASSESSMENTS AND FLOW CHART

8.1 Efficacy Measurements

Primary Efficacy Variable:

Duration of diarrhea (hours) between the start of treatment until the last watery/diarrheal stool before recovery or the end of study treatment (treatment duration maximal 5 days). Treatment will stop at recovery or after the morning dose of day 6, if not recovered.

Duration of diarrhea is defined as date and time of the evacuation of the final watery/diarrheal stool before recovery derived from the daily diary.

Secondary Efficacy Variables:

- Time until recovery, defined as date and time of the evacuation of the first of two consecutive normal stools or no stool within 12 hours after the first normal stool.
- Number of recovered subjects in total and until each individual treatment day.
- Global Physician Assessment (GPA) at the end of treatment, at the discretion of the investigator:
 - 1 = Complete relief of acute diarrhea,
 - 2 = marked improvement of acute diarrhea,
 - 3 = moderate improvement of acute diarrhea,
 - 4 = slight improvement of acute diarrhea,
 - 5 = no change in acute diarrhea,
 - 6 = worsening of acute diarrhea.(Treatment success = GPA score of 1 or 2).
- For toilet trained children only: number of stools per day as well as number of watery stools per day from start of treatment and until end of study treatment.

8.2 Safety Measurements

Adverse Events

Requirements for collecting, recording and reporting of AEs are described in Section 9. Each subject is to be evaluated at the termination visit. Should any AE be identified at this visit, the Investigator will continue to follow the subject as described in Section 9.1.2.

Vital Signs

Height and weight must be recorded.

Body temperature will be measured in the morning and in the evening with at least 12 hours interval. If the value is >39 degrees Celsius, the measurement has to be repeated within one hour to confirm the value.

Systolic blood pressure (SBP), diastolic blood pressure (DBP) and pulse rate are to be measured in pediatric appropriate setting.

Physical Examination

A physical examination should be performed and any relevant findings are to be recorded on the Medical History form in the CRF (for findings from the past that occurred prior to allocation to treatment), or on the Adverse Event form in the CRF for findings presently occurring.

8.3 Other Assessments

Informed Consent

Voluntary written informed consent must be obtained from one parent/legal representative prior to performing any study-related procedures (see Section 1.3).

Demographic Data

Demographic data (gender, age, year and month of birth, race) will be collected for all subjects.

Medical History

Any clinical event, including diagnosis, condition, or surgery, that occurred prior to allocation to treatment, is to be recorded on the Medical History form. In case a clinical event concerns a chronic disorder, which means it started in the past and it is still present at the screening visit, it should also be recorded on the Medical History Form. Examples of these events are diabetes, migraine, and hay fever.

Concomitant Medication

All medication taken by the subject during the study (from signing the informed consent form through post-study follow-up) is to be recorded on the Concomitant Medication form, except for study drug.

Subject Diary

The parent(s)/caregiver(s)/legal representative(s) have to document date and time of each individual stool of the subject and the stool consistency (watery, normal) of each evacuation continuously. The subject individual stool consistency before start of the diarrhea is defined as normal (e.g. taking into account the age and diet, e.g. breast feeding, of the individual subject).

Recording can be stopped after the excretion of two consecutive normal stools or no stool within 12 hours.

The date, time and dose of study drug intake as well as the amount ORS consumed has to be recorded.

Fever will be measured twice daily, once in the morning and once in the evening with at least 12-hour interval using the same device and method (preferably ear temperature), by the parent(s)/caregiver(s)/legal representative(s) and documented in the diary including method, time and value.

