
Methodology: This is a prospective, open-label, multicenter, single-arm study evaluating the efficacy and safety of Racecadotril in infants and children with acute diarrhea.
 
 
Open-label treatment
 <pre> graph LR V1[Visit 1, Day 1 Start treatment] --> T[Racecadotril + ORS] T --> V2[Visit 2, Day 6 Recovery or End of treatment] V2 --> FU[Safety Follow-up 5-7 days after V 2] </pre> 
 
Screening and Enrolment (Day 1, Visit 1) Subjects presenting with acute diarrhea will be evaluated for eligibility. They will undergo a physical examination including vital signs, a review of their medical history including vaccination history and concomitant medication. If the subjects are eligible, demographics, number of stools during the last 12 hours will be assessed as baseline values. On Day 1, the subject will start with study treatment. The starting dose will either be the noon or evening dose.
 
Treatment period (until recovery, maximally five days) Subjects will be treated with Racecadotril three times daily according to the body weight dose requirement on an out-patient basis for maximum 5 days in addition to ORS. ORS will be prescribed by the investigator. The parent(s)/caregiver(s)/legal representative(s) will be instructed to stop treatment when the patient recovered. Recovery is defined by the evacuation of the first of two consecutive normal stools or no stool within 12 hours. In the evening of each day, the parent(s)/caregiver(s)/legal representative(s) will fill in their diaries, documenting date and time of each individual stool, the stool consistency of each stool, ORS amount and the study drug intake. AEs are to be reported on an ongoing basis. Treatment will stop at recovery (last dose)
		

Name of Sponsor: Abbott Taiwan	Name of Finished Product: Hidrasec Infants Granules for Oral Suspension 10 mg Hidrasec Children Granules for Oral Suspension 30 mg	Name of Active Ingredient(s): Racecadotril
--	---	--

will be taken in the morning after recovery, ORS can be continued until Visit 2) or after the morning dose of day 6, if not recovered.

End of treatment (at recovery or Day 6, Visit 2)

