Subjects will be treated with Racecadotril three times daily according to the body weight dose requirement on an out-patient basis for maximum 5 days. The subjects will be treated with ORS (according to the registered local label and the instruction of the investigator) in addition to Racecadotril. ORS will be prescribed by the investigator and will be taken according to the product label and the instruction of the investigator. The parent(s)/caregiver(s)/legal representative(s) will be instructed to stop study drug treatment when the patient recovered. On each day, the parent(s)/caregiver(s)/legal representative(s) will fill in their diaries, documenting the date and time of each individual stool, the stool consistency of each stool (diarrheal/watery or normal), the amount of ORS, and the study drug intake. After the occurrence of two consecutive normal stools or no stool within 12 hours, the parent(s)/caregiver(s)/legal representative(s) can stop recording of the diary and return to the study site for the end of treatment visit. The date of recovery is the day when the first of two consecutive normal stools were excreted or the day

[figure not shown]
when no stool within 12 hours after the first normal stool was observed. AEs are to be reported on an ongoing basis.

End of treatment (Day 6 or early recovery, Visit 2)

The last dose of study drug will be the morning dose of day 6, if not recovered earlier (last dose will be the morning dose after recovery, ORS can be continued until Visit 2). On the same day, or within 24 hours after recovery (in exceptional cases within 48 hours), the parent(s)/caregiver(s)/legal representative(s) will visit the site for the end of treatment visit of the child. Data on vital signs, AEs, physical examination and concomitant medication will be collected. Subjects will return their diaries and unused medication.

Safety follow-up

A phone call will be performed 5-7 days after the end of the treatment period for the safety follow-up.

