8.6 Flow Chart of Study Assessments

All study assessments will be conducted as indicated in Table 2, which displays the frequency and timing of all measurements.

Table 2: Flow Chart of Study Assessments

Period	Screening	End of Treatment period	Safety follow-up (phone call 7 days after Visit 2)
Visit	1	2	3
Day	1	6²	11-13
Informed consent	X		
Inclusion/exclusion criteria	X		
Demographic data	X		
Medical history including vaccination history	X		
Physical examination	X	X	
Vitals signs	X	X	
Dispense study drug	X		
Concomitant medication	X	X	X
Compliance check		X	
Global physician assessment		X	
Adverse events	X	X	X
Collect study drug		X	
Dispense diary	X ¹		
Collect diary		X	

¹ Subjects' parent(s)/caregiver(s)/legal representative(s) have to fill in their daily diaries continuously.

² or within 24 hours (in exceptional justified cases within 48 hours) after recovery if this occurs before day 6

9 ADVERSE EVENTS**9.1 Adverse Events**Definition of Adverse Event

Any untoward medical occurrence in a patient or clinical investigation subject administered a pharmaceutical product and which does not necessarily have a causal relationship with this treatment. An AE can therefore be any unfavorable and unintended sign (including an abnormal laboratory finding, for example), symptom (including an AE occurring from drug abuse, an AE occurring from drug withdrawal and any failure of expected pharmacological action), or disease temporally associated with the use of a pharmaceutical product, whether or not considered related to the pharmaceutical product.

An elective surgery/procedure scheduled to occur during a study will not be considered an adverse event if the surgery/procedure is being performed for a pre-existing condition and the surgery/procedure has been pre-planned prior to study entry. However, if the pre-existing condition deteriorates unexpectedly during the study (e.g., surgery performed earlier than planned), then the deterioration of the condition for which the elective surgery/procedure is being done will be considered an adverse event.

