9.1 Primary Efficacy Variable

The primary efficacy variable is the duration (hours) of diarrhea (treatment duration max 5 days). Duration of diarrhea is defined as date and time of the evacuation of the last watery/diarrheal stool before recovery or end of treatment. The duration of diarrhea definition can be referred to Figure 9-1. The primary efficacy parameter, duration of diarrhea, will be analyzed using descriptive

statistics. In addition, a Kaplan-Meier plot will be generated for which summary statistics will be presented as well. The KM algorithm will be applied to derive the median duration (hours) and the 95% confidence intervals for the median, and mean duration. The censored number and event number will be presented as counts and percentage as well.

The SAS code is listed as below:

PROC LIFETEST DATA=duration METHOD=KM PLOTS=SURVIVAL (FAILURE ATRISK); TIME T*status (0); RUN;

[figure not shown]
Note:

[figure not shown]
The proc lifetest analysis will be performed with failure curve (an increasing trend). The duration (hours) of diarrhea or time (hours) until recovery is recorded in the variable T. The variable status is the censoring indicator. A status of 1 indicates an event time, and a status of 0 indicates a censored time. The event is recovery. The censored data are those did not recover during treatment period including drop-outs. When a patient doesn't recover beyond the end of study (treatment duration maximal 5 days), duration is stopped at the end of study date and it will be regarded as a censored data as well. The censored times will be plotted as a plus sign on the Kaplan-Meier.

An event time for the duration of diarrhea is defined as the duration from the date of dosing to the date of the evacuation of last watery/ diarrheal stool before recovery. A censored time for the duration of diarrhea is defined as the duration from the date of dosing to the date of not recovery during treatment period.

An event time for time until recovery is defined as the time from the date of dosing to the date of the evacuation of the first of two consecutive normal stools or no stool within 12 hours after the first normal stool. A censored time for time until recovery is defined as the duration from the date of dosing to the date of not recovery during treatment period.

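### The diary may be closed after 12 stool-free hours that directly follow a watery stool, but the recovery event in the analysis needs a normal stool first

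*Protocol*

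**What the plan says.** Two forms of the 12-hour criterion stand in the current text.

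**Without a prior normal stool.**
- Protocol 8.3, Subject Diary: "Recording can be stopped after the excretion of two consecutive normal stools or no stool within 12 hours".
- Protocol 4.1, the rule for ending the diary and returning for the end-of-treatment visit: "After the occurrence of two consecutive normal stools or no stool within 12 hours".
- Protocol synopsis, Treatment period: "Recovery is defined by the evacuation of the first of two consecutive normal stools or no stool within 12 hours". The same part of the synopsis has treatment stop at recovery, with a last dose the next morning.

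**With a prior normal stool.**
- Protocol 8.1, time until recovery: "the first of two consecutive normal stools or no stool within 12 hours after the first normal stool". The same condition appears in the synopsis list of secondary variables, in Protocol 3.2 and 10.3, and in SAP 2.2, 3.6, 9.1 and 9.2.1.
- Protocol 4.1, the date of recovery, in the same paragraph as the looser diary rule: the day "when no stool within 12 hours after the first normal stool was observed".

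SAP 9.1 makes recovery the Kaplan-Meier event for both duration of diarrhea and time until recovery: "The event is recovery. The censored data are those did not recover during treatment period including drop-outs". It defines duration by the "date and time of the evacuation of the last watery/diarrheal stool before recovery or end of treatment". Visit 2 takes place on Day 6, "or within 24 hours (in exceptional justified cases within 48 hours) after recovery if this occurs before day 6" (Protocol 8.6, footnote 2). Footnote 1 of the same table and section 8.3 ask for the diary to be kept continuously.

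**The concern.** The rule that ends data collection is looser than the rule that defines the event. A child whose last recorded stool was watery, and who then passes nothing for 12 hours (overnight, for example), satisfies the diary rule but not the event definition. The record can therefore end at a point where the event has not occurred and can no longer be observed.

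Three results depend on it: event or censoring status in both Kaplan-Meier analyses, the number and proportion recovered by day (SAP 9.2.2), and, if diarrhea resumes after the diary is closed, the time of the last watery stool. Treatment may also stop early, because the synopsis ties stopping to its own unqualified definition of recovery.

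**Working it through.** **1. The plan's own figure.** Protocol 10.8 and SAP 4.4 give n = 40, 99% recovery after 3 days and a precision of 3.1 points. The normal-approximation half-width is 1.96 × √(0.99 × 0.01 / 40) = 0.0308, or 3.1 points, so the figure reproduces.

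**2. One child under both definitions.** The times are assumed and counted from a first dose on Day 1 at 12:00.

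| Event | Clock | Hours |
|---|---|---|
| Last recorded stool, watery | Day 2, 20:00 | 32 |
| 12 stool-free hours complete, diary closed | Day 3, 08:00 | 44 |
| Visit 2 at the latest, normal window (24 h from closure) | Day 4, 08:00 | 68 |
| Latest possible end of treatment | Day 6, 08:00 | 116 |

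- Synopsis: recovered.
- SAP 9.1, read literally: no normal stool, so no event, and the child is censored.
- Descriptive duration: 32 h under either definition, because the last watery stool on record is the same.
- If a watery stool between 44 h and 68 h goes unrecorded, the 32 h is too short on the SAP definition, by more than 44 − 32 = 12 h and by at most 68 − 32 = 36 h.

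**3. Recovered proportion.** One child is 1/40 = 2.5 points overall and 1/20 = 5 points in an age group of 20. Exact (Clopper-Pearson) 95% intervals, if all other children recover:

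| Recovered | Proportion | 95% CI |
|---|---|---|
| 40/40 | 100% | 91.2–100 |
| 39/40 | 97.5% | 86.8–99.9 |
| 38/40 | 95.0% | 83.1–99.4 |
| 36/40 | 90.0% | 76.3–97.2 |
| 20/20 | 100% | 83.2–100 |
| 19/20 | 95.0% | 75.1–99.9 |

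**4. Kaplan-Meier summaries.** The documents give no distribution of durations, so one is assumed: 40 values at the log-normal quantiles (i − 0.5)/40, log-SD 0.5, medians of 24, 36 and 48 h, capped at 110 h. Randomly drawn children are changed from event to censored, either 12 h after the last watery stool or at 116 h.

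| Assumed median | Median shift, 1 child | Median shift, 4 children | Mean shift, 1 child |
|---|---|---|---|
| 24 h | 0 to 0.8 h | 0 to 3.2 h | −0.4 to 1.6 h |
| 36 h | 0 to 1.2 h | 0 to 4.9 h | −0.6 to 2.5 h |
| 48 h | 0 to 1.5 h | 0 to 6.5 h | 0 to 2.4 h |

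The mean is restricted to the largest event time. These are extremes. On average the median moves by less than 1 h for one child and by roughly 1.5 to 3.5 h for four.

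**The case against.** **The short form may be shorthand.** In Protocol 4.1 it is followed at once by the qualified recovery date, and the synopsis gives the full form in its list of variables. This is plausible, but no text says so, and a caregiver acting on the looser wording would still close the diary too soon.

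**Diaries are to be filled in continuously, and a last dose is still due after recovery, so the diary may remain in use.** This is a fair limit. However, section 8.3 expressly permits recording to stop once the trigger is met, and a general instruction to record continuously does not withdraw that permission.

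**The SAP is consistent.** This stands. A reader might infer that the SAP leaves such a child unclassified. The visible text does not support that: wherever the SAP defines recovery it requires the normal stool, and it censors those who do not recover. The conflict lies between the protocol's diary and synopsis wording and the event definition. SAP Figure 9-1, which illustrates the definitions, is not visible; it might confirm the classification but could not restore unrecorded stools.

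**The effect is small.** Largely true. The study is descriptive and single-arm, with no test or threshold to overturn, and the sample size calculation is unaffected. A reader might also extend the missed-stool error to 60 h by using the exceptional 48-hour visit window (44 + 48 − 32). That is not established. The last dose is the morning dose after recovery, which SAP 10.1 describes as the first dose of the next day. On that reading treatment in the example ends at about 68 h, and a later stool arguably falls outside the endpoint.

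**Conclusion.** The inconsistency is real and should be fixed. By following the protocol, a caregiver can end the record, and under the synopsis the treatment, before the event that the SAP analyses can be observed. The same child is then recovered under one document and censored under the other.

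The impact is modest and its frequency unknown. It is clearest for the recovered proportion, at 2.5 points per child in 40. It is slight for the Kaplan-Meier median unless several children are affected; both the durations and the four-child case are assumptions. A reader might infer that the primary endpoint as a whole is undermined. It is not: the descriptive duration is the same under both definitions and goes wrong only if a watery stool after closure is missed, by up to about 36 h on the assumed clock.

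**What to change.** Take one of two routes for the diary:

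1. Have caregivers record every stool until Visit 2, when the diary is already collected. The cost is normally up to 24 h of extra entries. A child who has passed no further stool by Visit 2 would still lack the event, but nothing up to that visit would have been lost.
2. In Protocol 4.1 and 8.3, let the diary stop only after two consecutive normal stools or 12 stool-free hours after the first normal stool, and otherwise on Day 6. A child who passes no further stool would keep recording until Day 6 at most.

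Under either route, bring the synopsis recovery sentence into line with the SAP definition. This has a cost to weigh: a child who passes no further stool would stay on treatment until Day 6 at most.

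No extra visit, new endpoint or larger sample is needed. A sentence in SAP 9.1 confirming that 12 stool-free hours directly after a watery stool is not an event would be helpful but is optional, since the text already implies it.
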